6.1.5. SAEs

6.1.5.1. Primary Analysis

Endpoint: Proportions of subjects reporting SAEs.

- Analysis time points: Through 12 months after Vaccination 1.
- Analysis population: Safety population (Primary Study Cohort - Stage 1).
- Analysis methodology: Descriptive summary statistics.
- Supporting objective: Primary safety objective.

Reporting Results:

The percentage (%), the number of subjects (n), the denominator (N) used in the percentage calculation, and the corresponding 95% Clopper-Pearson CI for subjects reporting any SAEs, each SOC, and each PT within SOC will be presented for each vaccine group.

Figures: None.

6.1.5.2. Additional Summary for Assessing SAEs

To support the assessment of SAEs, similar endpoints as above will be summarized for the Primary Study Cohort - Stage 2 through 12 months after Vaccination 2; as well as for the RSV Vaccine Month-0, Month-2 Cohort through 12 months after Vaccination 2 and through 14 months after Vaccination 1.

Listings of these SAEs will be provided by SOC and PT.

6.1.6. MAEs

MAEs will be analyzed in a similar way as SAEs ([Section 6.1.5](#)).

6.2. Secondary Endpoint(s)

6.2.1. RSV A– and RSV B–Neutralizing Antibody Titers

6.2.1.1. Primary Analysis

Endpoint: RSV A– and RSV B–neutralizing antibody titers.

- Analysis time points: Before and 1 month after Vaccination 1.
- Analysis populations: Evaluable immunogenicity population (Primary Study Cohort - Stage 1).
- Analysis methodology: Descriptive summary statistics.

- Supporting objective: Secondary immunogenicity objective.

Reporting Results:

GMTs before and 1 month after Vaccination 1, and associated 2-sided 95% CIs, will be summarized by vaccine group for both RSV A– and RSV B–neutralizing antibody titers. Also, GMFRs from before to 1 month after Vaccination 1, and associated 2-sided 95% CIs, will be summarized by vaccine group for both RSV A– and RSV B–neutralizing antibody titers.

Figures:

RCDCs for RSV A– and RSV B–neutralizing antibody titers for the 2 time points (before Vaccination 1 and 1 month after Vaccination 1) will be generated by vaccine group.

6.2.1.2. Additional Analysis

For the Primary Study Cohort - Stage 1, GMTs at all other applicable visits after Vaccination 1 but before Vaccination 2 will be summarized along with associated 2-sided 95% CIs, by vaccine group, for both RSV A– and RSV B–neutralizing antibody titers.

Similarly, for the RSV Vaccine Month-0, Month-2 Cohort, GMTs at all applicable visits will be summarized with 2-sided 95% CIs.

For the Primary Study Cohort - Stage 2, GMTs at all applicable visits (including visits in Stage 1 and Stage 2) will be summarized with 2-sided 95% CIs.

It should be noted that the inclusion of each applicable blood sampling visit will not take the protocol-required visit window into consideration as long as subjects meet the evaluable immunogenicity population criteria.

Additionally, all fold rises specified in [Section 3.2.1](#) will be summarized with GMFRs and associated 2-sided 95% CIs.

The following comparisons will be made in order to:

1. Assess adjuvant effects:

For the Primary Study Cohort - Stage 1, GMTs at each post–Vaccination 1 visit will be compared between RSVpreF 240 µg + Al(OH)₃ + SIIV and RSVpreF 240 µg + SIIV; as well as between RSVpreF 240 µg + CpG/Al(OH)₃ + SIIV and RSVpreF 240 µg + SIIV. GMRs and associated 2-sided 95% CIs will be calculated for each post–Vaccination 1 visit in Stage 1.

2. Assess SIIV coadministration interference to immune response induced by RSVpreF 240 µg + CpG/Al(OH)₃:

This will combine 1-month post-Vaccination 1 NT data from the **Primary Study Cohort - Stage 1** and the **RSV Vaccine Month-0, Month-2 Cohort**.

GMTs at 1 month after Vaccination 1 for RSV A NT and RSV B NT will be compared between the RSVpreF 240 µg + CpG/Al(OH)₃ with SIIV group (**Primary Study Cohort - Stage 1**) and the RSVpreF 240 µg + CpG/Al(OH)₃-only group (**RSV Vaccine Month-0, Month-2 Cohort**). GMRs and associated 2-sided 95% CIs will be calculated.

For the 1-month postvaccination visit, GMT summaries from the **Primary Study Cohort - Stage 1** and the **RSV Vaccine Month-0, Month-2 Cohort** will be presented for each vaccine group together with pooled placebo data.

Analysis using the mITT population may be used if there is a large enough difference compared with the evaluable immunogenicity population.

Figures:

For the remaining 2 cohorts (Primary Study Cohort - Stage 2 and RSV Vaccine Month-0, Month-2 Cohort), RCDCs will be plotted for prevaccination and 1-month postvaccination visits only.

NT GMT kinetics will be plotted across all visits for each cohort.

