Due to the deficit in the originally planned subject enrollment, approximately 62 subjects aged 65-85 years will be randomized 1:1 to receive a dose of 240 µg RSV vaccine with CpG/Al(OH)₃ or placebo followed by a second dose 2 months later. Safety, tolerability, and immunogenicity will be evaluated. This cohort will be known as the RSV Vaccine Month-0, Month-2 Cohort. The subjects will be enrolled before the influenza season. There will be no concomitant SIIV administration.

2. Evaluate safety and immunogenicity of a second dose of RSV vaccine administered to the Primary Study Cohort - Stage 1 subjects, 12 months after the initial dose to determine whether the immune response supports annual vaccination.

The safety and immunogenicity data from C3671001 and Stage 1 of C3671002 will guide the decision on whether a second dose of the RSV vaccine will be evaluated in Stage 2. If Stage 2 proceeds, this cohort will be known as the Primary Study Cohort - Stage 2. If there are no substantial differences in immune responses between the CpG/Al(OH)₃ and Al(OH)₃ formulations, then development of the CpG/Al(OH)₃ formulation may cease, and Stage 2 will not proceed.

If the data support implementation of Stage 2, invited, consenting subjects will be revaccinated with the same dose and formulation of the RSV vaccine or placebo received at Visit 1, concomitantly with SIIV. The safety, tolerability, and immunogenicity of the second dose will be evaluated through 12 months after revaccination.

Additional information for this compound may be found in the single reference safety document (SRSD), which for this study is the investigator's brochure. The SRSD for the SIIV will be the product information for the country where the vaccine was procured.

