1. VERSION HISTORY

This statistical analysis plan (SAP) for Study C3671002 is based on the protocol (Amendment 3) dated 22 Aug 2019.

Table 1. Summary of Major Changes in SAP Amendments

Version/Date	Associated Protocol Amendment	Rationale	Specific Changes
1/15 Feb 2019	Original (09 Oct 2018)	Not Applicable	Not Applicable
2/09 Jun 2020	3 (22 Aug 2019)	
Changes to maintain consistency with the 2015 version of the SAP template.
 
Updates according to protocol amendment 3.
	
 Added a document footer specifying the 2015 version of the SAP template, which does not include estimands. Added text to clarify that the existing objectives and endpoints apply to the Primary Study Cohort - Stage 1. Added objectives, study design, endpoints, analysis sets and analyses, and summaries for the newly added 2 cohorts: Primary Study Cohort - Stage 2, which will evaluate revaccination of the Stage 1 subjects with the RSV vaccine and concomitant SIIV, and the RSV Vaccine Month-0, Month-2 Cohort, which will evaluate a 240-µg dose of the RSV vaccine with CpG/Al(OH)₃, but without SIIV (Section 2.1, Section 2.2, Section 3, Section 4, and Section 6). Added text regarding the initiation of Stage 2 vaccination (Section 2.2). Added text to explain safety data and blood sample collection (Section 2.2). Added a new algorithm for calculating fold rise (Section 3.2.1 and Section 5.3.2).

Table 1. Summary of Major Changes in SAP Amendments

Version/Date	Associated Protocol Amendment	Rationale	Specific Changes

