2.2. Study Design

This is a Phase 1/2, multicenter, randomized, placebo-controlled, observer-blind, dose- and formulation-finding study.

The study will evaluate the safety, tolerability, and immunogenicity of up to 7 different RSV vaccine candidates with bivalent formulations (RSV A and RSV B) at 3 dose levels of 60 µg of the prefusion RSV F antigens CCI [REDACTED] 120 µg CCI [REDACTED] and 240 µg CCI [REDACTED] formulated with aluminum hydroxide (Al[OH]₃) or CpG/Al(OH)₃, or a 240-µg RSV vaccine CCI [REDACTED] alone, when administered concomitantly with SIIV, or 240 µg formulated with CpG/Al(OH)₃ on a Month-0 and Month-2 schedule without SIIV.

The study is organized in the following cohorts:

1. The Primary Study Cohort - Stage 1 will evaluate 7 RSV vaccine doses/formulations given concomitantly with SIIV at Month 0.
2. The Primary Study Cohort - Stage 2 will evaluate revaccination of the Stage 1 subjects with the RSV vaccine and concomitant SIIV, administered at Month 12.
3. The RSV Vaccine Month-0, Month-2 Cohort will evaluate a 240-µg dose of the RSV vaccine with CpG/Al(OH)₃ given at Months 0 and 2. No concomitant SIIV will be given.

Male and female subjects 65 to 85 years of age will be enrolled. Subjects will be randomized equally across all dose groups in the primary cohorts. The RSV Vaccine Month-0, Month-2 Cohort will be randomized 1:1 to receive RSV vaccine or placebo.

Primary Study Cohort - Stage 1. Enrollment in the Primary Study Cohort - Stage 1 commenced in April 2019 and completed in June 2019. Approximately 250 subjects 65 to 85 years of age were equally randomized at Visit 1 to receive one of the 7 RSV vaccine doses/formulations or placebo (a total of 8 parallel groups), concomitantly with SIIV.

Primary Study Cohort - Stage 2. Prior to completion of Stage 1, subjects may be invited to participate in Stage 2. Safety and immunogenicity data obtained from the C3671001 and C3671002 studies will be used to determine whether Stage 2 will proceed and, if so, whether all or some of the RSV formulations will be evaluated.

Two protocol administrative change letters (PACLs) were distributed to the sites regarding initiation of Stage 2 vaccination. The first PACL, dated in January 2020, was to instruct the sites that all subjects would be revaccinated in Stage 2. The second PACL, dated in March 2020, was to instruct sites to postpone the initiation of Stage 2 until further notice because of the coronavirus disease 2019 (COVID-19) pandemic.

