4.1.2. Evaluable Immunogenicity Population

This analysis population will include subjects who:

- Are eligible (have signed informed consent and met all inclusion/not met any exclusion criteria) and were randomized into the study;
- Have received both the SIIV and RSV vaccine or placebo and SIIV as randomized;
- Have a Visit 2 (1 month after vaccination) blood draw for assay testing within 27 to 42 days after Visit 1 (after vaccine administration) (note: the 27- to 42-day interval is calculated as the Visit 2 date minus the Visit 1 date);
- Have at least 1 valid and determinate assay result for the 1-month post-Vaccination 1 visit;
- Have no major protocol violation as determined by the study clinician.

Major protocol violations will be determined by clinical review. A major protocol violation is a protocol violation that, in the opinion of the sponsor's study medical monitor, would materially affect assessment of immunogenicity, eg, subject receipt of a prohibited vaccine or medication that might affect immune response or a medication error with suspected decrease in potency of the vaccine. The sponsor's medical monitor will identify those subjects with protocol violations before any immunogenicity analysis is carried out.

The evaluable immunogenicity population will be the primary analysis population for the immunogenicity endpoints evaluated among this cohort. Subjects will be included in the vaccine group as randomized in the analysis, which, by the population definition, is equivalent to the vaccine group corresponding to the vaccine received.

The evaluable immunogenicity population will also be the primary analysis population for the cellular assay results reported from this cohort.

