4.3.2. Evaluable Immunogenicity Population

This evaluable immunogenicity population will include subjects who:

- Are eligible (have signed informed consent and met all inclusion/not met any exclusion criteria) and were randomized into the study;
- Have received both vaccinations at Months 0 and 2 as randomized;
- Have a Visit 4 (1 month after Vaccination 2) blood draw for assay testing within 27 to 42 days after Visit 3, inclusive (after vaccine administration) (note: the 27- to 42-day interval is calculated as the Visit 4 date minus the Visit 3 date);
- Have at least 1 valid and determinate assay result for the proposed analysis;
- Have no major protocol violation as determined by the study clinician.

Major protocol violations will be determined as described in [Section 4.1.2](#) by clinical review.

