5.2.2.3. Geometric Mean Ratio

The geometric mean ratio (GMR) will be calculated by transforming the group mean difference of the antibody levels in natural logarithm scale to original scale. Two-sided 95% CI is also computed by exponentiating the CIs from the natural log scales using 2-sample Student's t distribution for the mean difference of measures on the logarithmically transformed assay results.

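### The GMR meant to show SIIV interference with the RSV response compares two separately randomised cohorts and has no baseline-adjusted counterpart

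*SAP*

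**What the plan says.** SAP 6.2.1.2 (Additional Analysis, item 2) combines 1-month post-Vaccination 1 data from two cohorts to assess SIIV interference. It says that "GMTs at 1 month after Vaccination 1 for RSV A NT and RSV B NT will be compared between the RSVpreF 240", and the sentence goes on to name the two arms: the Stage 1 group given this dose with CpG/Al(OH)3 alongside SIIV, and the Month-0, Month-2 group given that product alone. SAP 6.3.3 does the same for IgG A and IgG B. The method is in SAP 5.2.2.3: a back-transformed difference of log means, with a CI from the two-sample Student's "t distribution for the mean difference of measures on the logarithmically transformed assay results". It has no covariate.

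The design is in SAP 2.2. Stage 1 was randomised to 8 groups, all with SIIV. The Month-0, Month-2 Cohort was randomised 1:1 to RSV vaccine or placebo, without SIIV.

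On timing, "Enrollment in the Primary Study Cohort - Stage 1 commenced in April 2019 and completed in June 2019" (SAP 2.2). The second cohort came with the protocol version on which the SAP rests: the SAP "is based on the protocol (Amendment 3) dated 22 Aug 2019". Of that cohort, Protocol 1.2 says "The subjects will be enrolled before the influenza season".

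On populations, the Stage 1 evaluable set (SAP 4.1.2) is tied to the compared sample: "Have a Visit 2 (1 month after vaccination) blood draw for assay testing within 27 to 42 days after Visit 1". The Month-0, Month-2 set (SAP 4.3.2) instead requires that subjects "Have received both vaccinations at Months 0 and 2 as randomized" and have an in-window Visit 4 draw. SAP 6.2.1.2 sets the visit windows aside for other draws once a subject is evaluable, and makes the wider population optional: "Analysis using the mITT population may be used if there is a large enough difference compared with the evaluable immunogenicity population".

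**The concern.** No subject was randomised to RSV vaccine with or without SIIV, so anything that differs between the cohorts is indistinguishable from an SIIV effect in this ratio. The protocol itself gives reasons why baseline RSV titers might differ. Protocol 1.2 describes RSV as seasonal in temperate climates and immunity after natural infection as short-lived. It places the start of Stage 1 in the southern hemisphere influenza season and the other cohort before an influenza season.

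A cohort difference could therefore be read as interference, or could mask it. This bears on concomitant use with influenza vaccine, which Protocol 1.2 anticipates. Baseline GMTs and GMFRs are planned, so an imbalance would be visible, but no adjusted between-group ratio with a CI is planned. Protocol 5.1.2 keeps the sponsor's study team blinded only until the 1-month data are available for analysis, so an adjustment chosen after seeing an imbalance would be open to the charge of being data-driven.

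**Working it through.** **Plan's own figures.** Neither document states a precision or power figure for this GMR. Group sizes agree with Protocol Table 4: 250/8 = 31.25 and 62/2 = 31, so the contrast is about 31 against 31. The sizing example in Protocol 9.1 also reproduces: 1 − 0.95^31 = 0.796, stated as 80%.

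**Enrolment gap.** From 30 June 2019 (latest possible end of Stage 1 enrolment) to 22 August 2019 (date of Amendment 3) is 53 days, so the gap is at least that. This shows that enrolment was sequential. It does not show that titers differ.

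**Effect of a baseline difference.** All inputs here are assumed, since the documents give no SD, correlation or cohort shift. Let F be the baseline GMT ratio between cohorts, rho the correlation of log titer before and after vaccination, and SDs equal at both visits. There is no true interference and the cohorts differ only through baseline.

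- Unadjusted GMR = F^rho
- Baseline-adjusted (ANCOVA) GMR = 1.00
- Ratio of GMFRs = F^(rho − 1)

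| F | rho | Unadjusted GMR | ANCOVA | GMFR ratio |
|---|---|---|---|---|
| 1.25 | 0.5 | 1.12 | 1.00 | 0.89 |
| 1.25 | 0.7 | 1.17 | 1.00 | 0.94 |
| 1.5 | 0.5 | 1.22 | 1.00 | 0.82 |
| 1.5 | 0.7 | 1.33 | 1.00 | 0.89 |

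With unequal SDs the unadjusted GMR is F^(rho × SDpost/SDpre). This gives 1.08 to 1.22 at an SD ratio of 0.7, and 1.16 to 1.45 at 1.3.

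**Limit of adjustment.** If the cohort difference instead carries unchanged through both visits, the unadjusted GMR is F (1.25 to 1.50), ANCOVA gives F^(1 − rho) (1.07 to 1.22) and the GMFR ratio is 1.00. The two adjusted estimates differ by the factor F^(1 − rho) in either case.

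**Precision.** The unadjusted 95% CI multiplies and divides the GMR by exp(t × SD × √(2/31)), with t = 2.00 on 60 df. For ANCOVA, SD is replaced by SD × √(1 − rho²) on 59 df, ignoring the small loss from imbalance.

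| Assumed ln SD | Unadjusted | ANCOVA, rho 0.5 | ANCOVA, rho 0.7 |
|---|---|---|---|
| 0.7 | 1.43 | 1.36 | 1.29 |
| 1.0 | 1.66 | 1.55 | 1.44 |
| 1.3 | 1.94 | 1.77 | 1.60 |

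**Selection.** The Month-0, Month-2 evaluable set conditions on events after the compared Visit 2 sample. Suppose 2 to 4 of 31 (6.5% to 12.9%) are lost after Visit 2, with loss correlated 0.3 to 0.5 with titer. That arm's GMT then moves by 2% to 6% at ln SD 1, and by 1% to 7% over ln SD 0.7 to 1.3. This is small beside the CI factors above.

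**The case against.** The strongest reply is that the plan follows the protocol. The Statistical Methods part of the Protocol Summary bases comparisons between vaccine groups and by cohort on ratios of postvaccination GMTs, and the study has no hypothesis test and no decision rule. That stands as a reason to keep the planned GMR. It does not bar an adjusted ratio beside it.

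A reader can also see an imbalance from the planned summaries, and could form a ratio of GMFRs from their published CIs. That is true, but it leaves the adjusted result to the reader and does not yield the ANCOVA estimate.

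The two adjusted estimators disagree by construction. This is correct, so one must be named in advance as the main adjusted result.

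The combined 1-month display pools the placebo groups, and a reader might infer that placebo drift between cohorts is hidden. The documents do not support that: each cohort's own NT and IgG summaries are by vaccine group (SAP 5.2, 6.2.1, 6.3.3), and pooled placebo does not enter this GMR.

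A reader might also infer serious selection bias from the mismatched evaluable sets. The mismatch is real, although SAP 6.2.1.2 does not name the population for item 2 and the evaluable sets are inferred from its surrounding sentences. The effect is small even under assumed informative loss. Protocol Table 3 gives Visit 2 a 28- to 35-day window, and SAP 6.5.2 summarises exclusions with reasons.

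**Conclusion.** The concern holds and is minor. That SIIV is fully confounded with cohort, and that the GMR has no baseline term, follow directly from the text. The size and direction of any distortion are unknown. The range 1.12 to 1.33 rests wholly on an assumed baseline difference, correlation and equal SDs, and each value in it is smaller than every unadjusted CI factor shown.

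Three stronger readings are not supported. The first is that the cohorts do differ at baseline, or that the GMR is biased in a known direction: the documents show separate enrolment, not different titers. The second is that a primary or secondary analysis is compromised. The Stage 1 arm does use the 1-month RSV NT data that form a secondary endpoint, but this contrast is an additional analysis under SAP 6, all analyses are descriptive (SAP 5.1.2), and no prespecified primary or secondary analysis changes. The third is that the study's assessment of RSV vaccine interfering with the SIIV response is affected. The Stage 1 HAI comparison in SAP 6.2.2.2 is between randomised groups of one cohort and is untouched.

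**What to change.** In SAP 6.2.1.2 item 2 and SAP 6.3.3:

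1. Keep the planned GMR. Beside it, prespecify a GMR adjusted for ln baseline titer (ANCOVA) with its 95% CI, for RSV A and B NT and IgG A and B, as the main adjusted result.
2. Report the between-group ratio of the planned GMFRs, with its CI, as a secondary sensitivity analysis.
3. State that the comparison is non-randomised and across cohorts, and that adjustment for baseline does not remove every cohort difference. Add no decision rule.
4. As a small sensitivity run, repeat the comparison with Month-0, Month-2 subjects selected on Vaccination 1 as randomised and a Visit 2 draw 27 to 42 days after Visit 1, mirroring SAP 4.1.2.

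Showing the placebo groups unpooled in the combined display is optional.

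The cost is SAP wording, four small models with their sensitivity versions, and one selection flag. The baseline sample is already defined (SAP 3.4.1) and scheduled in both cohorts. No new data are needed.

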Investigational sites will be notified which commercially available SIIV will be provided prior to the start of enrollment.

Placebo

The placebo will be a sterile normal saline solution for injection (0.9% sodium chloride injection, in a 0.5-mL dose).

Statistical Methods

The study sample sizes are not based on any formal statistical hypothesis testing. Statistical analysis will be descriptive in nature.

The safety analyses include local reactions, systemic events, AEs, medically attended AEs (MAEs), AEs of specific interest, and SAEs. AEs will be categorized according to the Medical Dictionary for Regulatory Activities (MedDRA). The counts and percentages will be provided for AEs and e-diary events, with 2-sided 95% exact CIs as appropriate.

For immunogenicity endpoints, geometric mean titer (GMT) and geometric mean fold rise (GMFR) from baseline will be calculated by vaccine group and by cohort along with the 95% confidence intervals. Relevant comparisons between vaccine groups and by cohorts will be based on the ratios of postvaccination GMTs, and the associated 2-sided 95% confidence intervals will also be constructed.

The percentages of subjects achieving seroprotection and seroconversion at 1 month after vaccination will be computed for each virus strain contained in SIIV separately.

Interim Analyses

Three interim analyses outlined in [Section 9.4](#) are planned before the final analysis at the completion of the study. The results of these analyses will be used to select the most appropriate dose(s), formulation(s), and dosing schedule of the RSV vaccine for use in further studies.

SCHEDULE OF ACTIVITIES

The Schedule of Activities table provides an overview of the protocol visits and procedures. Refer to the Study Procedures and Assessments sections of the protocol for detailed information on each procedure and assessment required for compliance with the protocol. The investigator may schedule visits (unplanned visits) in addition to those listed on the Schedule of Activities table, in order to conduct evaluations or assessments required to protect the well-being of the subject.

Table 1 Schedule of Activities applies to those subjects participating in the Primary Study Cohort - Stage 1 (single dose administration of RSV vaccine/placebo given concomitantly with SIIV). Study procedures for this cohort are fully described in [Section 6.1](#).

Visit Number	1	2 ^a	2	3	4	5 ^b

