5.2. General Methods

Safety data, immunogenicity data, and cellular assay data will be summarized by vaccine group for each cohort. All analyses will be descriptive in nature.

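### The cross-cohort test of influenza-vaccine interference with the RSV response is non-randomised and unadjusted, and the summaries beside it pool the two placebo groups that would show a cohort shift

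*SAP*

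**What the plan says.** SAP 6.2.1.2 names two between-group contrasts for RSV A and RSV B neutralising titre (NT).

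- **Adjuvant effect, within Stage 1.** Each adjuvanted 240 µg group is compared with unadjuvanted 240 µg: "GMRs and associated 2-sided 95% CIs will be calculated for each post–Vaccination 1 visit in Stage 1".
- **SIIV interference, across cohorts.** Of this contrast the SAP says "This will combine 1-month post-Vaccination 1 NT data from the" two cohorts. It compares 240 µg with CpG/Al(OH)₃ given with SIIV (Stage 1) and the same product given without SIIV (Month-0, Month-2 Cohort), at 1 month after Vaccination 1.

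SAP 6.3.3 plans only the second contrast for prefusion F IgG. In both sections the 1-month summary "will be presented for each vaccine group together with pooled placebo data".

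The two placebo groups differ. Stage 1 subjects received "one of the 7 RSV vaccine doses/formulations or placebo (a total of 8 parallel groups), concomitantly with SIIV" (SAP 2.2), and enrolled from April to June 2019. For the Month-0, Month-2 Cohort, added by the amendment dated 22 August 2019, Protocol 1.2 says: "The subjects will be enrolled before the influenza season. There will be no concomitant SIIV administration".

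The Protocol Summary (Statistical Methods) states: "Relevant comparisons between vaccine groups and by cohorts will be based on the ratios of postvaccination GMTs". It does not name placebo as a comparator. SAP 5.2 adds: "Safety data, immunogenicity data, and cellular assay data will be summarized by vaccine group for each cohort".

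**The concern.** The interference GMR equates a difference between cohorts with an effect of SIIV. Anything else that separates the cohorts goes into the same ratio:

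- calendar time;
- assay run (SAP 7.2 expects assays to arrive in batches);
- evaluability. Stage 1 requires a Visit 2 draw (SAP 4.1.2). The other cohort requires both doses and a Visit 4 draw (SAP 4.3.2), so its 1-month post-Vaccination 1 sample is not held to a window.

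The placebo groups received no RSV antigen. If SIIV alone does not move RSV antibody, the ratio of their titres estimates the non-SIIV shift directly. Pooling them removes that check from the summaries where the two cohorts are set side by side.

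The second gap is that vaccine is never set against concurrent placebo as a ratio with an interval for RSV NT or IgG. The SAP does plan placebo contrasts for HAI titres (6.2.2.2), H3N2 neutralisation (6.3.5) and cellular assays (5.2.2.5, 6.3.1). As a result, the Month-0, Month-2 Cohort has no randomised between-group estimate of RSV antibody response. SAP 7.2 nevertheless uses the interim results to select dose, formulation and schedule.

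**Working it through.** **The plan's own figures.** The documents state no precision or power for RSV antibody. Their only operating characteristic is Protocol Table 11, on adverse events. It reproduces: 1 − 0.95^31 = 0.796, stated as 0.80. It does not bear on this point.

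**Inputs.** Group size is 31 (Protocol Table 4: about 31 per Stage 1 group, target 31 per Month-0, Month-2 arm), with everyone taken as evaluable. The method is a two-sample t interval on the natural-log scale without covariates (SAP 5.2.2.3). The ln-titre SD is not in the documents; I assume 0.6 to 1.2. Cohort shifts of 1.25, 1.5 and 2.0 are also assumptions.

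**Formulas.**

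- SE = SD × √(2/31) = 0.254 × SD.
- 95% CI factor = exp(t × SE), with t = 2.00 on 60 df.
- With a true SIIV effect of 1 and a cohort shift s, the t statistic is noncentral with parameter ln(s)/SE. For s = 1.5, ln(s) = 0.405, so the parameter is 0.405/0.152 = 2.66 at SD 0.6 and 0.405/0.305 = 1.33 at SD 1.2.

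**Probability that the interference GMR's CI excludes 1 with no SIIV effect.**

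| ln-SD | SE | CI factor | shift 1.25 | shift 1.5 | shift 2.0 |
|---|---|---|---|---|---|
| 0.6 | 0.152 | 1.36 | 0.30 | 0.75 | 0.99 |
| 0.8 | 0.203 | 1.50 | 0.19 | 0.50 | 0.92 |
| 1.0 | 0.254 | 1.66 | 0.14 | 0.35 | 0.77 |
| 1.2 | 0.305 | 1.84 | 0.11 | 0.26 | 0.61 |

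Without a shift, each probability would be 0.05.

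**What the pooled row shows.** With equal groups whose placebo GMTs differ s-fold, the pooled GMT lies √s from each: √1.5 = 1.22 and √2 = 1.41. It represents neither cohort.

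**Precision of the proposed additions.** Placebo against placebo, and vaccine against own placebo, are both 31 versus 31. Their CI factors are those in the table, 1.36 to 1.84. Dividing one cohort's vaccine/placebo ratio by the other's would cancel a common shift, but the SE rises to SD × √(4/31) and the factor to 1.53–2.35.

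**The case against.** The strongest reply is that little is actually lost. Placebo is a vaccine group in each cohort. In Stage 1, SAP 6.2.1.1 has GMTs and fold rises that "will be summarized by vaccine group for both RSV A– and RSV B–neutralizing antibody titers", and 6.2.1.2 and 6.3.3 do the equivalent for the other cohorts. A reader can find both placebo GMTs with their intervals. The study is descriptive, with no hypotheses or decision rules. Protocol 9.2.2 specifies GMRs only for HAI, so the SAP breaks no promise. The pooled wording may not even rule out separate placebo rows alongside.

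Much of this stands, and it rules out several stronger readings:

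- *RSV results are never compared with placebo.* Not so. Vaccine and placebo are shown together within each cohort; what is missing is the ratio and its interval.
- *Pooling hides any cohort shift.* It masks one only in the NT and IgG cross-cohort summaries.
- *The pooled row biases an estimate.* It enters no planned contrast, so the 1.22 and 1.41 factors describe a displayed row only.
- *The second cohort belongs to another season.* The documents give no actual enrolment dates for it. They support later, non-concurrent enrolment and no more.

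What the reply does not meet is that the interference GMR is itself a planned between-group estimate with an interval, and it carries no safeguard where it is presented. Comparing separate intervals by eye across tables is a poor substitute for the ratio.

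**Conclusion.** The point holds as one of presentation and missing estimates; it does not invalidate any result. The interference GMRs for NT and IgG cannot separate SIIV from cohort, and the summaries beside them drop the available negative control. A 1.5-fold shift would look like an SIIV effect with probability about 0.26 to 0.75. That range rests on the assumed SDs, the assumed shift and 31 evaluable per group; the documents do not show that any shift exists.

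The negative control also has limits. At 31 versus 31 the placebo ratio would itself detect a 1.5-fold shift only with those same probabilities, so a placebo ratio near 1 with a wide interval is weak reassurance. It also assumes that SIIV alone leaves RSV antibody unchanged.

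The absence of any RSV NT or IgG ratio against concurrent placebo is a clear gap, most of all in the Month-0, Month-2 Cohort.

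**What to change.** 1. In SAP 6.2.1.2 and 6.3.3, replace the pooled placebo data with one placebo row per cohort.
2. Beside each interference GMR, report the Stage 1 placebo / Month-0, Month-2 placebo GMR with its 95% CI, and label the interference GMR as a non-randomised cross-cohort comparison.
3. Add descriptive NT and IgG GMRs of each vaccine group against its own cohort's placebo, at least at the 1-month post-vaccination visits.

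The samples and assays are already planned, so the cost is SAP wording and output. With four assays (NT A and B, IgG A and B), item 3 adds 7 × 4 = 28 ratios in Stage 1 and 1 × 4 × 2 visits = 8 in the Month-0, Month-2 Cohort. Item 2 adds 4, for 40 in all, plus up to 28 if Stage 2 runs with all groups. Extending Stage 1 to every post-vaccination visit (1, 3, 6 and 12 months) would mean 7 × 4 × 4 = 112, which is why the 1-month visits are the sensible minimum. The downside is more intervals without multiplicity adjustment, so they should be marked as descriptive.
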